SAMPLE SIZE ESTIMATE	
Phase I/Dose Escalation: Expected 6, but up to 12 subjects to identify the MTD. Subjects enrolled to Phase 1 who withdraw for reasons other than toxicity during the dose-limiting toxicity (DLT) period will be determined to be not evaluable and will be replaced.
 
Phase II/Dose Expansion: 34 additional subjects
 
For sample size determination, we assume the following:
 
Null hypothesis: 1-yr RFS=75%
 
Alternative hypothesis: 1-yr RFS=0.90
 
Alpha=0.1 (one-sided)
 
Beta=0.1 (power=90%)
 
Total accrual=40 evaluable subjects.
 
Anticipate accrual of 6 evaluable subjects from phase I component of study.
 
34 subjects to accrue in phase II portion of study.
 
Assuming 10% non-evaluable rate, 44 subjects would be accrued to the efficacy component of the study to yield 40 evaluable subjects. Subjects enrolled to Phase 2 who withdraw for toxicity during the initial lead-in cycle will be determined to be not evaluable and replaced.

DURATION OF TREATMENT AND STUDY PARTICIPATION	The study is expected to take approximately 36 months from first subject enrolled to last subject follow-up, including approximately 12 months of enrollment period, an estimated 5 months of treatment.

TABLE OF CONTENTS

PROTOCOL SYNOPSIS.....	3
LIST OF ABBREVIATIONS AND DEFINITIONS OF TERMS.....	11
1. INTRODUCTION.....	15
1.1. Soft Tissue Sarcoma.....	15
1.1.1. Epidemiology	15
1.1.2. Standard Treatment	15
1.1.3. Use of radiotherapy in adjuvant and neo-adjuvant therapy.....	16
1.1.4. Use of chemotherapy in adjuvant and neo-adjuvant therapy	17
1.1.5. Use of chemoradiotherapy in adjuvant and neo-adjuvant therapy.....	19
1.2. Cabozantinib Background	22
1.3. Rationale for Combination of Cabozantinib with Radiation Therapy for High-Risk Soft Tissue Sarcoma of the Extremities.....	23
1.4. Rationale for Starting Dose Selection.....	24
2. STUDY OBJECTIVES AND ENDPOINTS	25
2.1. Objectives	25
2.1.1. Primary Objectives.....	25
2.1.2. Secondary Objective(s)	25
2.1.3. Exploratory Objective(s)	25
2.2. Endpoints	25
2.2.1. Primary Endpoints	25
2.2.2. Secondary endpoints	25
2.2.3. Exploratory endpoints	26
3. STUDY DESIGN	27
3.1. Dose-finding Phase 1 Portion of the Study:.....	27
3.2. Dose Expansion Phase 2 Portion of the Study:.....	28
3.3. Study Duration, End of Study, End of Treatment, End of Treatment Visit, Follow-up Period.....	28
4. STUDY POPULATION	30
4.1. Number of Subjects	30
4.2. Inclusion Criteria.....	30

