3.2. Dose Expansion Phase 2 Portion of the Study:

The dose-expansion Phase 2 will be conducted using an open-label, single stage design. Subjects enrolled in the Phase 1 dose-escalation component of the study at the RP2D level and meeting all inclusion/exclusion criteria for the Phase 2 component of the study will be included for efficacy and safety evaluation in the Phase 2 efficacy component of the study.

Subjects enrolled to the dose-expansion Phase 2 portion of the study will receive one week of cabozantinib monotherapy at the RP2D prior to initiating radiation therapy. Starting at Cycle 1 Day 8, subjects will initiate therapy concurrently with radiation therapy. Subjects enrolled to phase 2 who withdraw prior to initiation of radiation therapy will not be considered evaluable and will be replaced. A window of ± 7 days is permitted for initiation of RT in relation to C1D8. It is recommended that subjects begin treatment on a Monday due to radiation scheduling, however this is not mandatory. At least 7 days must pass between C1D1 and initiation of radiation therapy.

3.3. Study Duration, End of Study, End of Treatment, End of Treatment Visit, Follow-up Period

The study is expected to take approximately 60 months from first subject enrolled to last subject follow-up, including approximately 36 months of enrollment period, an estimated 5 months of treatment (or until treatment is no longer tolerated).

End of Treatment (EOT) for a subject is defined as the date of the last dose of cabozantinib. End of Treatment Visit for a subject is when safety assessments and procedures are performed after the date of the last dose of cabozantinib.

30-Day Follow-Up for a subject is defined as 30 days (± 1 week) after the last dose of cabozantinib. This visit will include safety assessments.

Follow-up period is the on-study time period after the EOT Visit.

The End of Study (EOS) defined as either the date of the last visit of the last subject to complete the study, or the date of receipt of the last data point from the last subject that is required for primary, secondary, and/or exploratory analysis, as pre-specified in the protocol, whichever is later.

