12.2. Efficacy Analysis

Assessment of the primary efficacy analysis will take place in real time. Based on anticipated accrual of 40 evaluable subjects, if 9 or more have relapsed or died due to any cause (unless clearly documented as unrelated to investigational diagnosis, e.g., car accident) at or before one year after cabozantinib initiation, then the study will be closed to further accrual, and data will simply be collected on the remaining subjects, as specified in the protocol.

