12.4. Sample Size Considerations

Phase 1: up to 12 subjects to identify the MTD, but the MTD may be reached with as few as 5 subjects.

Phase 2: For sample size determination, we assume the following:

- Null hypothesis: 1-yr relapse-free survival (local and distant) =75%
- Alternative hypothesis: 1-yr relapse-free survival (local and distant) =90%
- Alpha=0.1 (one-sided).
- Beta=0.1 (power=90%)

Total accrual=40 evaluable subjects.

Anticipate accrual of 6 evaluable subjects from phase I component of study. Therefore, 34 evaluable subjects to accrue in phase II portion of study. Subjects who withdraw for reasons other than toxicity during the DLT Period will be determined to be not evaluable and will be replaced.

Subjects are evaluated for efficacy assessment if they receive at least one dose of cabozantinib in combination with neoadjuvant radiation therapy.

Assuming a 10% drop-out/non-evaluable rate, 44 total subjects would be accrued to the efficacy component for the study to yield 40 evaluable subjects.

From the perspective of efficacy, this study is intended as a screening study of activity. Thus, avoiding a type II error (rejecting the proposed regimen as inactive, when it is an active regimen) is a major consideration. This study is not intended to provide definitive evidence of activity. Therefore, a type I error (false positive) is not considered as critical. For these reasons, we have chosen to increase the power of the study to 90% (minimizing type II errors), while relaxing constraints regarding type I. Specifically, we use a one-sided alpha of 0.10 for rejection of the null hypothesis. Use of a one-sided value is justified based on the high efficacy for *local* control of soft tissue sarcoma provided by the combination of surgery and neoadjuvant radiation therapy (~90%). It is not anticipated that distant disease control would be worsened by addition of cabozantinib to neoadjuvant radiation therapy.

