An early stopping rule for accrual to the efficacy component of the study is to be undertaken. If 9 (nine) or more evaluable subjects are found to have died or demonstrated disease recurrence at or before 1 (one) year after cabozantinib initiation, then the efficacy component of the study will be discontinued. This assumes of a binomial probability for the primary endpoint, with a target probability of 0.90 for evaluable subjects to be alive and disease-free at one-year after initiation of cabozantinib therapy. When 9 subjects demonstrate failure with respect to the primary endpoint (disease recurrence or death from any cause), then the upper bound of the 95% confidence interval for the binomial probability distribution would no longer encompass the target probability of 0.90 ($31/40=0.775$, 95%CI:0.62-0.89). At this point, the study would be considered negative with respect to the primary endpoint, and further accrual will be discontinued.

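### The nine-failure accrual stop is a valid single count set for 40 subjects, but with no earlier boundary it acts late

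*Combined protocol and SAP*

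**What the plan says.** Section 12.2 says the primary efficacy outcome is assessed in real time and gives the rule: "Based on anticipated accrual of 40 evaluable subjects, if 9 or more have relapsed or died due to any cause" within a year of starting cabozantinib, the study closes to further accrual. Section 12.4 presents this as an early stopping rule for accrual and derives the count. With nine failures the estimate is 31/40 = 0.775, 95% CI 0.62–0.89, and the upper limit "would no longer encompass the target probability of 0.90". No count is given for a smaller number enrolled, and no operating characteristics of the stop are stated.

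The design inputs in section 12.4 are "Null hypothesis: 1-yr relapse-free survival (local and distant) =75" per cent and "Alternative hypothesis: 1-yr relapse-free survival (local and distant) =90" per cent, one-sided alpha 0.10, power 90% and 40 evaluable subjects. Section 3.2 describes a single-stage design.

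The enrolment period differs between sections. The Synopsis has the study "including approximately 12 months of enrollment period", while section 3.3 has it "including approximately 36 months of enrollment period".

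**The concern.** A rule that protects subjects during accrual has to be able to act while accrual is open. At that time fewer than 40 are enrolled, and a poor regimen may already show a failure count whose interval excludes the 90% target. One count derived at 40 does not respond to this. The endpoint also takes up to a year to occur, so with fast enrolment most subjects are entered before many failures can be seen. At stake is how many further subjects enter a neoadjuvant, curative-intent trial after the data already speak against the target.

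**Working it through.** **Inputs.** From section 12.4: null 0.75, target 0.90, one-sided alpha 0.10, power 0.90, 40 evaluable subjects, stop at nine failures. Enrolment is 12 months (Synopsis) or 36 months (section 3.3). Imaging is every 12 weeks (section 6.2.5).

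**1. The plan's own figure.** The exact (Clopper–Pearson) upper limit for x successes of n is the 0.975 quantile of Beta(x+1, n−x).
- 31/40 gives 0.615–0.892, which matches the stated 0.62–0.89.
- 32/40 gives an upper limit of 0.909.

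Nine is therefore the smallest excluding count at n = 40.

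**2. Nine failures at smaller n.** The upper limit is 0.769 at n = 20, 0.853 at n = 30, 0.889 at n = 39 and 0.892 at n = 40. It passes 0.90 only at n = 44 (0.902). Nine failures are thus sufficient at any n up to 40.

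**3. Smallest count that meets the same criterion at smaller n.**

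| Subjects | 10 | 15 | 20 | 25 | 30 | 35 | 40 |
|---|---|---|---|---|---|---|---|
| Failures | 4 | 5 | 6 | 7 | 8 | 8 | 9 |

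Nine is first needed at n = 37.

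**4. When the rule acts.** This was simulated with 40 subjects entering uniformly, failure times uniform over months 3–12 (in brackets, 0–12) and no detection delay. The documents give neither the failure-time pattern nor an RFS of 60%; both are assumptions.

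| True RFS | Enrolment | Accrual stopped before 40 |
|---|---|---|
| 75% | 12 months | about 1% (4%) |
| 75% | 36 months | about 35% (41%) |
| 60% | 12 months | 10% (35%) |
| 60% | 36 months | 91% (94%) |

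With exponential failure times instead, the 75% rows become 5% and 43%. If failures are seen only at 12-weekly scans, they become 1% and 37%. Timing aside, nine failures are reached at all with probability P(≥9 of 40 | failure rate 0.25) = 0.700.

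**5. Cost of earlier boundaries, exactly.** The documents state no critical value for the primary test. The alpha implies success at ≥34 of 40: P(X ≥ 34 | 40, 0.75) = 0.0962 and P(X ≥ 34 | 40, 0.90) = 0.9005.

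Let w(n, f) be the probability of f failures among the first n subjects without a stop. Then w(n, f) = p·w(n−1, f) + (1−p)·w(n−1, f−1), and at each look the mass at or above the boundary is removed. False stop is the total mass removed at p = 0.90. Power is the mass left at n = 40 with f ≤ 6.

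| Boundaries | False stop at 90% | Power |
|---|---|---|
| 9 of 40 only | 0.0155 | 0.9005 |
| 6 of 20, 8 of 30, 9 of 40 | 0.0234 | 0.8994 |
| 4 of 10 added to these | 0.0312 | 0.8949 |
| criterion at every n from 5 to 40 | 0.061 | 0.883 |

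**6. Gain from looks at 20 and 30** (same assumptions as step 4).
- 36 months, 75%: mean enrolled falls from about 38 (37) to 34 (33).
- 36 months, 60%: from about 30 (29) to 24 (23).
- 12 months, 75%: from 40.0 to 39.6 (39.8 to 39.0), with early stops in 8% (15%) of trials.
- 12 months, 60%: early stops rise from 10% (35%) to 39% (58%).

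**The case against.** The strongest defence is that nine is a proper best-case curtailment. It treats every other planned subject as a success, so the conclusion holds whenever the ninth failure occurs. That is correct. A reader might infer that the rule lacks a denominator, or that its interval applies only once all 40 are enrolled. The documents support neither reading: both sections tie nine to 40, and step 2 shows the interval is lower still at smaller n.

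A reader might also infer that the plan breaches its own criterion by continuing to enrol after, say, six failures of 20. The design is single-stage, and section 12.4 evaluates the interval only at the planned total. It never promises to recompute the interval as subjects enter. Carrying the criterion to smaller n is a proposal of this review, not a rule the plan breaks.

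Section 12.4 gives priority to avoiding a type II error, and a late stop for poor activity fits that. This argument rules out monitoring at every n, which would take power to 0.883. It does not count against two looks that cost about 0.1 point.

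There is other oversight as well. Section 16.1 has committees review accrual and stopping rules at least annually, and section 14.5 allows termination at any time. This mitigates the problem but gives those committees no earlier threshold to apply.

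**Conclusion.** The rule is valid but late, and adding boundaries is a cheap improvement rather than the repair of an error. Under the null of 75% it seldom shortens accrual if enrolment takes 12 months (about 1–4% of trials). It does so in roughly a third to two-fifths of trials if enrolment takes 36 months.

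To say it never acts would be too strong. At an assumed RFS of 60% over 36 months it stops accrual in more than nine trials in ten, though after about 30 subjects on average.

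The benefit of earlier looks depends on the enrolment period: about four fewer subjects at 75% and six fewer at 60% over 36 months, but under one at 75% over 12 months. The exact limits, false-stop probabilities and power need no timing assumption, though power takes success as ≥34 of 40. The timing results rest on uniform entry, the assumed failure-time spread, prompt detection, and all 40 treated as one stream although about six are expected from phase 1.

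**What to change.** In sections 12.2 and 12.4, keep nine failures overall and add two boundaries on evaluable subjects in enrolment order: stop accrual if ≥6 of the first 20 or ≥8 of the first 30 have failed. Count subjects with pending outcomes as not failed; this is conservative and lets either boundary act as soon as the count is reached.

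State the operating characteristics: false stop at 90% RFS 0.0234 (0.0155 with nine alone) and power 0.8994 (0.9005 with nine alone), together with the success count used for power. Do not apply the criterion at every n, and leave out a look at 10, which would bring power to 0.895.

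Reconcile the 12- and 36-month enrolment periods, since they largely decide whether any boundary can act. Use one definition of failure for all boundaries: section 12.2 leaves out deaths clearly documented as unrelated to the sarcoma, while section 12.4 counts every death.

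The cost is one small table, about 0.1 point of power (0.9005 − 0.8994 = 0.0011) and 0.8 point more false stops (0.0234 − 0.0155 = 0.0079). No extra subjects or visits are needed.

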12.5. Primary Analysis

This will occur once all data for primary and secondary endpoints is collected.

13. WITHDRAWAL FROM TREATMENT, PROCEDURES, AND STUDY

13.1. Discontinuation from Investigational Product or Study

Subjects may discontinue study treatment or withdraw their consent to participate in the study at any time without prejudice. The investigator may withdraw a subject from study treatment or from the study if, in his or her clinical judgment, it is in the best interest of the subject or if the subject cannot comply with the protocol.

In addition, any of the following conditions require discontinuation of the subject from study treatment:

- An AE or intercurrent illness that in the opinion of the investigator warrants the subject's withdrawal from study treatment;
- The investigator believes it is not in the best interest of the subject to continue on study
- Specific conditions described in the Management of Adverse Events Section 10.2.2;
- Necessity for treatment with other anticancer treatment prohibited by protocol;
- Sexually active subjects who refuse to use medically accepted barrier methods of contraception (e.g., male condom, female condom) during the study and for 4 months after discontinuation of study treatment;
- Women who become pregnant or are breastfeeding;
- If the subject does not recover from his or her toxicities to tolerable Grade ≤ 2 within 6 weeks, the subject will have study treatment discontinued unless there is unequivocal evidence that the subject is benefitting. In this situation, a subject may be able to restart therapy with a dose reduction upon resolution of the toxicity and with agreement of the principal investigator;
- Request by regulatory agencies for termination of treatment of an individual subject or all subjects under the protocol;
- Significant noncompliance with the protocol schedule in the opinion of the investigator;
- Subjects who cannot tolerate the minimum protocol-specified dose of study treatment will have study treatment discontinued;
- Progressive disease (PD) or the subject no longer experiences clinical benefit as determined by the investigator

13.2. Sponsor-Investigator Decision to Withdraw or Terminate Subject's Participation Prior to Study Completion

The Sponsor-Investigator can decide to withdraw a subject(s) from Investigational Product and/or other protocol-required therapies, protocol procedures, or the study as a whole at any time prior to study completion.

Subjects may be eligible for continued treatment with Exelixis' Investigational Product and/or other protocol-required therapies by a separate protocol or as provided for by the local country's regulatory mechanism.

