 - a. Females of child-bearing potential (FOCBP) must agree to use highly effective contraception without interruption from initiation of therapy and continue until 4 months (120 days) after last dose of study therapy. FOCBP must have a negative serum pregnancy test (β -hCG) result at screening and agree to ongoing pregnancy testing during the study, and at the end of study treatment. A highly effective method of contraception is defined as one that results in a low failure rate (that is, $<1\%$ per year), when used consistently and correctly, such as implants, injectables, combined oral contraceptives, some intrauterine contraceptive devices, sexual abstinence, or a vasectomized partner (APPENDIX 1 - WOMEN OF CHILDBEARING POTENTIAL DEFINITIONS AND METHODS OF CONTRACEPTION).
 - b. Male subjects must practice abstinence or agree to use a condom during sexual contact with a pregnant female or a female of childbearing potential while participating in the study (APPENDIX 1 - WOMEN OF CHILDBEARING POTENTIAL DEFINITIONS AND METHODS OF CONTRACEPTION).
7. Life expectancy of >3 months, as determined by the investigator.
8. Ability to understand and sign informed consent.
9. Willingness and ability to comply with scheduled visits, laboratory tests, and other study procedures.

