11.1. Permitted Medications and Procedures

The investigator must be informed as soon as possible about any medication taken from the time of screening until the 30 Day Follow-Up visit. Any concomitant medication(s), including herbal preparations, taken during the study will be recorded in the CRF. The minimum requirement is that drug name, dose, and the dates of administration are to be recorded. Additionally, a complete list of all prior cancer therapies will be recorded in the CRF.

Subjects should receive full supportive care during the study, including transfusions of blood and blood products, and treatment with antibiotics, anti-emetics, anti-diarrheas, and analgesics, and other care as deemed appropriate, and in accordance with their institutional guidelines. WBC growth factors may be administered at the discretion of the investigator, consistent with institutional guidelines.

Extreme precaution must be taken with contraceptives (either combined or progesterone only), as it is not known if there is the potential of inhibition/induction of enzymes that affect the metabolism of estrogens and/or progestins.

- Antiemetics and antidiarrheal medications are allowed prophylactically according to standard clinical practice if clinically indicated.
- Granulocyte colony-stimulating factors (G-CSF or GM-CSF) are allowed if used per clinical guidelines (e.g., ASCO or ESMO guidelines).
- Bisphosphonates can be used to control bone loss or hypocalcemia if the benefit outweighs the risk per the investigator's discretion.
- Transfusions and hormone replacement should be utilized as indicated by standard clinical practice.
- Individualized anticoagulation therapy with heparin is allowed if it can be provided safely and effectively under the following circumstances:
 - *Low dose heparins for prophylactic use* are allowed if clinically indicated and the benefit outweighs the risk per the investigator's discretion.
 - *Therapeutic doses of LMWH at the time of the first dose of study treatment* are allowed if the subject has no evidence of brain metastasis, has been on a stable dose of LMWH for at least 6 weeks, and has had no complications from a thromboembolic event or the anticoagulation regimen.

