20. APPENDIX 1 - WOMEN OF CHILDBEARING POTENTIAL DEFINITIONS AND METHODS OF CONTRACEPTION

20.1. Definitions

20.1.1. Woman of Childbearing Potential (WOCBP)

A woman is considered fertile following menarche and until becoming postmenopausal unless permanently sterile. Permanent sterilization methods include hysterectomy, bilateral salpingectomy, and bilateral oophorectomy.

Women in the following categories are not considered WOCBP

- Premenarchal
- Premenopausal female with 1 of the following:
 - Documented hysterectomy
 - Documented bilateral salpingectomy
 - Documented bilateral oophorectomy

Note: Documentation can come from the site personnel's review of the participant's medical records, medical examination, or medical history interview.
- Postmenopausal female
 - A postmenopausal state is defined as 12 months of amenorrhea in a woman over age 45 years in the absence of other biological or physiological causes.

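### The mandatory contraception stop in Section 13.1 tests refusal of barrier methods, so it misses a woman who drops her required highly effective method but accepts condoms

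*Combined protocol and SAP*

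**What the plan says.** Section 13.1 introduces its list by saying that "any of the following conditions require discontinuation of the subject from study treatment". One item on the list is "Sexually active subjects who refuse to use medically accepted barrier methods of contraception (e.g., male condom, female condom) during the study". The same item extends the period to 4 months after treatment ends. It is not limited by sex, by childbearing potential or by any other method in use.

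The contraception required of subjects is set elsewhere:

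- **Women of childbearing potential.** Under Inclusion 6a they "must agree to use highly effective contraception without interruption from initiation of therapy", up to 4 months after the last dose. Appendix 20.2 requires one method from its highly effective list. It puts male and female condoms under a separate, less than highly effective heading.
- **Other women.** Appendix 20.1.1 removes sterilised and postmenopausal women from the childbearing-potential group. No contraception is asked of them.
- **Men.** Under Inclusion 6b they either abstain or "agree to use a condom during sexual contact with a pregnant female or a female of childbearing potential while participating in the study". For men with partners of childbearing potential, Appendix 20.3 requires a condom until 4 months after the last dose. It offers abstinence or a condom where the partner is pregnant or breastfeeding.

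Section 11.1 separately urges extreme caution with combined and progesterone-only contraceptives, because it is not known whether there is an effect on the enzymes that metabolise them.

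**The concern.** A mandatory stopping rule on contraception should enforce the contraception that the protocol requires. This one is keyed to a class of methods that Appendix 20.2 ranks below the required class. For women of childbearing potential it can therefore err in both directions: silent when the required method is lost, and triggered when the required method is in place.

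The first direction matters more. Section 1.2 describes cabozantinib as embryotoxic and as causing fetal malformations in rats. A woman who has lost her highly effective method is the person for whom an automatic rule would be most useful.

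What is at stake is continued cabozantinib and fetal exposure to it. Radiation is given as standard care (Section 7.2), resection is already planned (Inclusion 1), and subjects who stop the drug stay in follow-up (Section 6.4.2).

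**Working it through.** The plan gives no figure on this point, so the check sets the texts side by side.

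**Methods in Appendix 20.2.** The highly effective methods are combined hormonal, progestogen-only hormonal, implant, intrauterine device (IUD), hormone-releasing intrauterine system (IUS), bilateral tubal occlusion, vasectomised partner and abstinence. That is 8 methods, of which 0 are barriers. Without abstinence, 8 − 1 = 7.

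**Reach of the Section 11.1 caution.** It covers combined, progestogen-only and implant methods, so 3 of the 7, or 4 if the IUS is counted (the documents do not say). Outside it are 7 − 4 = 3 (IUD, tubal occlusion, vasectomised partner), or 7 − 3 = 4 with the IUS left out. The IUD is taken as non-hormonal because the IUS is listed separately. These are counts of methods, not of subjects.

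**Cases.**

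| Subject | Inclusion 6 and Appendix 1 | Section 13.1 bullet |
|---|---|---|
| Woman of childbearing potential gives up her highly effective method, accepts condoms | Not met | Not triggered |
| Same group, non-hormonal highly effective method, declines condoms | Met | Triggered: must stop |
| Same group, hormonal method, declines condoms | Met | Triggered; the Section 11.1 caution offers a possible reason |
| Sexually active man, partner of childbearing potential, refuses condoms | Not met | Triggered: the texts agree |

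**What else reaches the first case.**

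1. The opening of 13.1 lets the investigator withdraw a subject if "it is in the best interest of the subject or if the subject cannot comply with the protocol". This is permissive.
2. The best-interest bullet in 13.1 is a mandatory stop, but only once the investigator has formed that view.
3. The noncompliance bullet concerns the protocol schedule and rests on the investigator's opinion.
4. Section 13.2 adds that "The Sponsor-Investigator can decide to withdraw a subject(s) from Investigational Product". This too is permissive.
5. Pregnancy itself is a mandatory stop (Sections 9.2.2 and 13.1). Serum tests fall on Day 1 of each 21-day cycle. With a window of 3 days either side of each visit, the gap between tests runs from 21 − 3 − 3 = 15 days to 21 + 3 + 3 = 27 days, assuming no cycle is delayed. A test can find a pregnancy only after it has begun.

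Items 1 to 4 depend on judgement, and item 5 acts late. No mandatory rule is tied directly to loss of the required method.

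**The case against.** A reader might infer that the two parts of the protocol contradict each other on who must come off the drug. The documents do not support that. Only Section 13.1 says who must stop; Inclusion 6 and Appendix 1 say what must be used, and neither forbids a barrier. A subject who adds a condom to her required method satisfies both.

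A reader might also infer that a postmenopausal or sterilised woman, or a man whose partner cannot conceive, must stop cabozantinib for declining a condom. That strains the text: the bullet concerns contraception, and where conception is impossible there is nothing to prevent.

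Nor is the woman who drops her method wholly unaddressed. The requirement is continuing, not just an entry test. Appendix 20.2 calls for discussion of alternative highly effective methods if she forgoes abstinence, and the best-interest bullet compels a stop once the investigator reaches that judgement.

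Finally, a blanket barrier rule could be a deliberate safety choice, given the reproductive toxicity and the caution on hormonal contraceptives. That is a fair reason for hormonal users, and simply deleting the barrier would remove a possible safeguard for them. It is weaker for the 3 or 4 methods outside the caution. Section 11.1 itself asks for no barrier, and neither Inclusion 6a nor Appendix 20.2 mentions one as a back-up.

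All of this narrows the point. It does not answer the case where the required method is lost and condoms are accepted.

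**Conclusion.** The point holds in a limited form, at low severity. The mandatory stop is tied to a different requirement from the one the protocol imposes. Its main fault is that it does not respond when a woman of childbearing potential replaces her highly effective method with condoms. Its lesser fault is that, on a literal reading, it stops cabozantinib in a woman who meets Inclusion 6a with a non-hormonal method.

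The number affected cannot be derived. It is probably very small, because the bullet needs an active refusal and the uncovered case needs a change of method during treatment. Sample size, alpha, power and the early stopping rule for efficacy are unchanged, so any inference that the trial's results are at risk is unsupported.

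The conclusion rests on the protocol text alone. The consent pages were not available and may ask for a barrier. Confidence is high on the difference in wording, and lower on how often it would matter in practice.

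**What to change.** Reword the Section 13.1 bullet to: *Sexually active subjects who refuse, or stop without replacing, the contraception required of them by Inclusion 6 and Appendix 1 (for women of childbearing potential, a highly effective method; for men with a pregnant, breastfeeding or childbearing-potential partner, a condom or abstinence)*, followed by the bullet's present time period, unchanged. Adding the words on stopping without replacement brings in a lapse that involves no outright refusal.

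Two accompanying edits keep the change clean:

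- If the barrier is meant as a back-up for women using hormonal methods, state it in Inclusion 6a and Appendix 20.2. Subjects then agree to it before enrolment, and the reworded bullet enforces it.
- Align Inclusion 6b with Appendix 20.3. The first offers abstinence in all cases and runs only while the man is in the study. The second names abstinence only for pregnant or breastfeeding partners and runs to 4 months after the last dose. Without this, the reworded bullet would carry that mismatch into a mandatory stop.

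The cost is a small wording amendment and a check of the consent form. No visit, test or analysis is added.
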